5.3.2.2 Secondary endpoints and additional [REDACTED] MDS-UPDRS based endpoints

The analysis approach and the MMRM model as described for the primary endpoint will be performed for additional MDS-UPDRS based endpoints as listed below, except that, 1) the baseline MDS-UPDRS I+II+III total score term in the model will be replaced by the corresponding baseline value of MDS-UPDRS total or sub-part score being analyzed, 2) MCP-MOD dose-response may be performed, 3) no additional multiple comparison adjustment will be applied for secondary efficacy [REDACTED] endpoints

- MDS-UPDRS Parts I, II, III (**Secondary Efficacy Endpoints**),
- MDS-UPDRS Parts II+III, Ib+II+III

- Postural Instability -Gait Difficulty (PIGD) score (mean score of MDS-UPDRS items 2.12+2.13+3.10+3.11+3.12),
- Lower Extremity (LE) score (mean score of MDS-UPDRS items 3.10+3.11+3.12+3.13+3.3d+3.3e+3.7a+3.7b +3.8a+3.8b+3.17c+3.17d+2.12+2.13), and Tremor score (mean score of MDS-UPDRS items 2.10+3.15a+3.15b+3.16a+3.16b+3.17a+3.17b+3.17c+3.17d+3.17e+3.18).

5.3.2.3 Sensitivity analysis

A sensitivity analysis will be conducted for MDS-UPDRS based endpoints, by including the data after PD medication assessed in the “OFF” status, that is, the assessment was made at least 12 hours since the last time the subject took the medication, or assessed in the “off” status by the rater, or if subject reported not taking PD medication at that visit.

The analyses will be performed based on the same MMRM model as described for the primary endpoint, except the following:

- An unstructured covariance matrix will be used to model the within-subject variance-covariance errors (instead of random intercept and slope). If the unstructured covariance structure matrix results in a lack of convergence, the heterogeneous Toeplitz covariance structure followed by the heterogeneous first-order autoregressive covariance structure will be used.

[figure not shown]
The table below summarizes the detailed information.

		Primary analyses		Sensitivity analyses	
MDS-UPDRS endpoints	Type	MMRM model covariance structure	Data after PD medications included (Y/N)	MMRM model covariance structure	Data after PD medications included (Y/N)
I+II+III	Primary	Based on random slope and intercept	N	Based on pre-specified covariance structure (UN if no convergency issue occurs)	Y
I	Secondary		N		Y
II	Secondary		N		Y
III	Secondary		N		Y
██████	██████		█		█
██████	██████		█		█
██████	██████		█		█

5.3.2.4 Early Parkinson’s Regional Progression Score (EP-RPS) measure

The Early Parkinson’s Regional Progression Score (EP-RPS) measure is a novel method of assessing disease progression based on a modified scoring algorithm for the MDS-UPDRS Part III items that is potentially more reliable and sensitive to progression in early stages of PD, as compared with change in MDS-UPDRS Part III total score. The new concept has been developed to capture the spread of the progression of disease symptoms across body regions as a reflection of the underlying topographic spread of pathology. [Figure 5.1](#) shows a general diagram of the concept of EP-RPS and the detailed definition are provided in Appendix IV.

Figure 5.1: Diagram of the concept of EP-RPS measure

EP-RPS will be summarized and analyzed by using ANCOVA model. The model will include the endpoint as the outcome, fixed effect of treatment group (categorical) and adjust for region (categorical), baseline PD subtype (categorical), baseline MDS-UPDRS Part III total score (continuous) and baseline striatum SBR values (continuous). Least square means (LSmeans) of each treatment group as well as treatment difference between BIIB054 groups and placebo will be displayed with 95% CI and p-value at Week 52. MDS-UPDRS Data after the PD medication will be included and excluded in two separate analyses, since this endpoint is unknown, though expected to be minimally impacted by PD medications and including the data will reduce the amount of missing data.

Spearman’s correlation of this endpoint with change from baseline at Week 52 in MDS-UPDRS Part III will be calculated.

CONFIDENTIAL

The information contained herein may not be used, disclosed, or published without the written consent of Biogen MA Inc.

[Redacted]

[Redacted]

[Redacted]

[Redacted]

[Redacted]

[Redacted]

[Redacted]

[Redacted]

[REDACTED]

5.3.2.8 Subgroup analysis

Subgroup analyses will be performed for the outcomes of MDS-UPDRS part III and I+II+III respectively in the subgroups of the following baseline covariates. The MMRM model is the same as the one in the primary analyses. If the MMRM model of a specific subgroup does not converge, no results will be displayed for that subgroup. A forest plot will be generated to present the results of all subgroups together.

- Age (above v.s. below median)
- Gender (male v.s. female)
- region, (US v.s. Other)
- prior use of PD medication (Yes v.s. No)
- time since onset of PD symptoms (above v.s. below median)
- baseline type of PD (tremor-dominant v.s. PIGD-dominant v.s. Indeterminate)
- baseline MDS-UPDRS III (above v.s. below median)
- baseline MDS-UPDRS I+II+III (above v.s. below median),
- baseline modified H&Y stage (≤ 1.5 v.s. ≥ 2)
- [REDACTED]
- baseline total striatum SBR measure, occipital reference ($\leq \text{mean-sd}$ v.s. $> \text{mean-sd}$ to $\leq \text{mean+sd}$ v.s. $> \text{mean+sd}$)
- baseline contralateral putamen SBR measure, occipital reference ($\leq \text{mean-sd}$ v.s. $> \text{mean-sd}$ to $\leq \text{mean+sd}$ v.s. $> \text{mean+sd}$)
- baseline ipsilateral putamen SBR measure, occipital reference ($\leq \text{mean-sd}$ v.s. $> \text{mean-sd}$ to $\leq \text{mean+sd}$ v.s. $> \text{mean+sd}$)
- [REDACTED]
- [REDACTED]
- [REDACTED]
- baseline total striatum volume (above v.s. below median),
- baseline lateral ventricle volume (above v.s. below median),
- [REDACTED]
- [REDACTED]
- baseline stride time variability (above v.s. below median),

Subgroup analysis will be performed respectively by including and excluding data after PD medication. The forest plot will be generated respectively as well. Besides, subgroup analysis of time to start of PD medication will be performed for the subgroup of regions (US v.s. Italy v.s. Other)

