5 STATISTICAL ANALYSIS METHODS

5.1 General Considerations

Summary tables will be presented using descriptive summary statistics. For continuous variables, summary statistics will generally include: number of subjects with data, mean, standard deviation, median, and range (minimum and maximum). For categorical variables, this will generally include: number of subjects randomized or dosed, number with data, and the percent of those with data in each category.

Unless otherwise specified, baseline value is defined as the most recent non-missing measurement collected prior to the first dose. Change from baseline will be defined as post-baseline value minus baseline value.

Statistical testing will be performed to assess efficacy endpoints by conducting pairwise comparison between each BIIB054 group and placebo, and no multiplicity will be adjusted. Unless stated otherwise, all the statistical tests will be 2-sided with a statistical significance level of 0.05 .

The statistical software, SAS[®] will be used for all summaries and analyses.

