5.3.2 MDS-UPDRS

5.3.2.1 Primary efficacy endpoint

Estimand:

The estimand of the primary analysis is the mean difference of the change from baseline in MDS-UPDRS I+II+III total score at Week 52 between treatment groups in the ITT population in a hypothetical setting where subjects do not start PD medication. MDS-UPDRS data collected after the intercurrent events, i.e., subjects start PD medication will be excluded in the primary analysis. Specifically, the estimand takes the following into consideration:

- A. Population: ITT population as defined in Section 5.1.2
- B. Variable: change from baseline to Week 52 in MDS-UPDRS score
- C. Intercurrent events: had PD medication not been made available to subjects prior to Week 52
- D. Population-level summary: difference in variable means between treatment conditions.

CONFIDENTIAL

The information contained herein may not be used, disclosed, or published without the written consent of Biogen MA Inc.

MMRM will be used as the primary analysis to analyze the change from baseline in MDS-UPDRS score. The model includes the fixed effects of treatment group, time (categorical), baseline PD subtype (categorical; PIGD vs TD vs indeterminate), prior use of PD medication (categorical), treatment group-by-time interaction, region (categorical), baseline MDS-UPDRS I+II+III total (continuous), baseline MDS-UPDRS I+II+III total by time interaction and baseline striatum SBR values (continuous), and baseline striatum SBR by time interaction. A random intercept and slope will be included in the model to model the random effects within subjects. If small sample size in subgroups of PD types causes lack of model convergence, the indeterminate group will be combined with the TD group. The Kenward-Roger approximation will be used to estimate the denominator degrees of freedom. Least square means (LSmeans) of each treatment group as well as treatment difference between BIIB054 groups and placebo will be displayed with 95% CI and p-value at Week 52. If the distribution of the outcome is highly skewed, p-value will be generated from the MMRM model based on ranked data. In the primary analysis, missing data are assumed to be missing at random (Rubin 1976), and MDS-UPDRS I+II+III score is impacted by PD medication.

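### Year 1 SAP 5.3.2.8 shows subgroup results only from separate within-subgroup MMRM fits; no visible text estimates or tests whether the treatment effect differs between subgroup levels

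*SAP*

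**What the plan says.** Section 5.3.2.8 of the Year 1 SAP covers MDS-UPDRS Part III and Parts I+II+III. On the model it says "The MMRM model is the same as the one in the primary analyses". The fits are separate, because the next rule reads "If the MMRM model of a specific subgroup does not converge, no results will be displayed for that subgroup". The display is fixed by "A forest plot will be generated to present the results of all subgroups together", and the whole set is doubled by "Subgroup analysis will be performed respectively by including and excluding data after PD medication". A typical factor is "Age (above v.s. below median").

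The primary model in 5.3.2.1 has no treatment-by-subgroup term. Its least-squares means and dose-placebo differences "will be displayed with 95% CI and p-value at Week 52". Section 5.1 describes efficacy testing "by conducting pairwise comparison between each BIIB054 group and placebo, and no multiplicity will be adjusted", and sets the default: "Unless stated otherwise, all the statistical tests will be 2-sided with a statistical significance level of 0.05". Section 5.3.2.1 also calls the pairwise p-values nominal and applies error control only to the MCP-MOD p-value.

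The visible text of 5.3.2.8 contains no interaction term or test, no rule for interpreting a difference between levels, and no statement that the results are exploratory. It does not mention p-values either.

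**The concern.** A subgroup analysis asks whether the effect of a dose differs between, say, younger and older subjects. That is a question about the difference between two estimates, and no visible output gives that difference, its confidence interval or a test of it. Two separate results, one with p below 0.05 and one above, do not answer it: each half has far less power than the whole trial, so one can easily miss while the other hits.

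In a Phase 2a trial, subgroup patterns can influence who is enrolled in the next study. Without a planned comparison between levels, the natural substitute is to see which intervals exclude zero, and that reading is unreliable at these sample sizes.

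**Working it through.** **Inputs (Year 1 SAP).** Section 4: placebo change 8.0, SD 10.64, maximum reduction 55%, so the full effect is 0.55 × 8.0 = 4.4 points at Week 52. Table 4.3: 91 / 48 / 90 / 90 evaluable subjects (placebo / 250 / 1250 / 3500 mg). Section 5.1: two-sided 0.05. Appendix III: the candidate dose-response models.

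**Check against the stated power.** A simulated MCP-MOD test with these inputs gives 81.5% average power at Week 52 with the seven Appendix III models and 80.9% with the five types named in Section 4, against the stated 80% or so. The printed active mean of 3.2 implies 8.0 − 3.2 = 4.8 points (60%) and gives 87–88%, so 4.4 is used and 4.8 is a sensitivity value.

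**One median split, a dose at the full effect.** Each half has about 45.5 placebo and 45 active subjects.
- SE = 10.64 × √(1/45.5 + 1/45) = 2.237; 4.4 / 2.237 = 1.967.
- Power per half: p = Φ(1.967 − 1.96) = 0.503.
- The halves are independent, so P(exactly one significant) = 2p(1 − p) = 2 × 0.503 × 0.497 = 0.500.
- Both significant: 25.3%. Neither: 24.7%.
- With 4.8 points: p = 0.574 and P(exactly one) = 0.489.

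The expression 2p(1 − p) cannot exceed 0.50, so this case sits at the maximum. Among simulated trials with exactly one significant half, an interaction test was also significant in about 10%. Under a uniform effect an interaction test at 0.05 signals 5% of the time by construction.

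**Other doses.** Section 4 lets the remaining arms lie anywhere between zero and the maximum. Each Appendix III shape was scaled so that its maximum over 0–3500 mg is 4.4 points, using half of each arm and the same formula:

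| Shape | Fraction of maximum at 250 / 1250 / 3500 mg | P(exactly one half) |
|---|---|---|
| Emax | 0.40 / 0.83 / 1.00 | 18% / 47% / 50% |
| Exponential 2850.5 | 0.04 / 0.23 / 1.00 | 10% / 14% / 50% |
| Logistic | 0.03 / 0.34 / 1.00 | 10% / 18% / 50% |
| Linear-log | 0.26 / 0.67 / 1.00 | 13% / 38% / 50% |
| Quadratic | 0.19 / 0.75 / 0.84 | 12% / 43% / 47% |
| Exponential 860.5 | 0.01 / 0.06 / 1.00 | 10% / 10% / 50% |
| Linear | 0.07 / 0.36 / 1.00 | 10% / 19% / 50% |
| Average | | 12% / 27% / 50% |

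The mean over doses is (12 + 27 + 50) / 3 ≈ 29–30%. With no effect at all the figure is 2 × 0.05 × 0.95 = 9.5%.

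**Sensitivity.** For a large arm, a true effect of 3.6 points gives 46% and 2.4 points gives 31%. If 30% or 50% of data are lost to PD medication (assumed; the SAP gives no fraction), the full-effect figure is 47–49% or 41–44%, across 4.4 and 4.8 points.

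**Number of comparisons.** Visible factors: 11 with two levels and 4 with three, so 22 + 12 = 34 levels. Then 34 × 2 outcomes × 2 data sets × 3 doses = 408. With no drug effect, 408 × 0.05 ≈ 20 would fall below 0.05. Both are upper figures for the visible factors: they need every fit to converge and every p-value to be reported.

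**The case against.** A reader might infer that the SAP judges subgroup effects by testing at 0.05 within each level. It does not say so. The only stated display in 5.3.2.8 is a forest plot, which can be read from its intervals without any test. The p-values and the 0.05 level come from 5.3.2.1 and 5.1, and 5.3.2.1 calls the pairwise p-values nominal. Error control is confined to the MCP-MOD result at Weeks 52 and 72, so no subgroup result can support the trial's efficacy claim. All of this stands. It limits what a subgroup result can be used for, but it does not supply the missing comparison between levels.

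A reader might also take 50% as the general rate. It is the ceiling, reached by a dose at the full effect in an equal split. Four of the 11 two-level factors (gender, region, prior PD medication, Hoehn and Yahr stage) are not median splits, and lower doses give much smaller figures under most candidate shapes.

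The lack of an exploratory label is weak evidence by itself. Parts of the Year 1 SAP are blacked out, including bullets in this section, and a label could sit there or in the protocol. The point does not rest on it.

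Finally, interaction models across four arms have low power and can run into convergence trouble in sparse cells. That is fair, and it belongs in the cost of the change.

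**Conclusion.** The point holds as an inexpensive improvement to a secondary display. On the visible text, 5.3.2.8 plans separate fits and nothing that estimates or tests a treatment-by-subgroup difference. If significance is compared between levels, a uniform effect would look confined to one half of a median split up to about 50% of the time for a full-effect dose, and about 30% averaged over doses and candidate shapes, against 5% for an interaction test. These figures assume equal halves, the Section 4 effect and SD, Table 4.3 numbers and a normal approximation, and they apply per dose-placebo comparison. The documents do not support saying that the plan prescribes that reading, or that about 20 false positives will be reported. The primary analysis is not affected.

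**What to change.** For each factor, fit one MMRM on the full ITT set, adding subgroup, subgroup-by-time, treatment-by-subgroup and treatment-by-subgroup-by-time terms. Beside the forest plot, report the Week 52 treatment-by-subgroup difference with its 95% CI and the interaction p-value. State that subgroups are exploratory and are interpreted from that estimate, not from significance within a level.

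Use fewer or merged levels where cells are sparse. For the SBR factors cut at mean ± SD, each tail would hold about 16% of subjects if values were roughly normal (an assumption): 0.16 × 90 ≈ 14 per large arm and 0.16 × 48 ≈ 8 at 250 mg. A single model also avoids refitting the primary covariates for region, PD subtype and prior PD medication within levels where they do not vary.

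The cost is SAP wording and modest programming. The downside is low power. For two equal halves the SE of the difference is 2.237 × √2 = 3.164, so a true difference of 4.4 points between halves would be detected with power of about Φ(4.4/3.164 − 1.96) = Φ(−0.57) ≈ 28%. Most subgroup results will read as inconclusive, which is what these numbers can support.

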5.3.2.9 Per-protocol analysis

The per-protocol analysis will be performed in the same fashion as the primary analysis for MDS-UPDRS I+II+III, but by applying in the per-protocol population as defined in Section 4.1. If the per-protocol population is largely the same as the ITT population, i.e., $\geq 90\%$ of subjects included in the ITT population are also included in the per-protocol population, then the per-protocol analysis will not be performed.

5.3.3 Other clinical efficacy endpoints

Other clinical efficacy (function) and quality of life assessments are listed as below. The questionnaire as well as the scoring algorithm for these clinical assessments are described in Appendix I.

- [REDACTED]
- [REDACTED]
- [REDACTED]
- [REDACTED]
- [REDACTED]
- [REDACTED]
- [REDACTED]
- [REDACTED]
- [REDACTED]
- [REDACTED]
- [REDACTED]
- [REDACTED]
- [REDACTED]
- [REDACTED]
- [REDACTED]
- Clinical Global Impressions Improvement (CGI-I) Scale (collected at Week 52 in the US sites only)*,
- Patient Global Impression of Change (PGI-C) (collected at Week 52 in the US sites only)*.

Data after PD medication will be included in the analysis for all the outcomes except [REDACTED].

For each clinical assessments that are collected longitudinally, an MMRM model will be used to analyze the change from baseline in the continuous clinical outcome, with addition of adjustment for the corresponding baseline outcome value and its interaction with time. i.e. the model will include fixed effects of treatment group (categorical), time (categorical), region (categorical), treatment group-by-time interaction, baseline value of the corresponding outcome (continuous), baseline value of the outcome by time interaction, baseline MDS-UPDRS I+II+III total score (continuous), baseline MDS-UPDRS I+II+III total score-by-time interaction, baseline striatum SBR values (continuous), and baseline striatum SBR by time interaction. The endpoints listed with a “*” next to them, will additionally include the baseline PD subtype (categorical) as a covariate. An unstructured covariance matrix will be used to model the within-subject variance-covariance errors. If the unstructured covariance structure matrix results in a lack of convergence, the heterogeneous Toeplitz covariance structure followed by the heterogeneous first-order autoregressive covariance structure will

CONFIDENTIAL

The information contained herein may not be used, disclosed, or published without the written consent of Biogen MA Inc.

be used. Least square means (LSmeans) of each treatment group as well as treatment difference between BIIB054 groups and placebo will be displayed with 95% CI and p-value at Week 52.

For CGI-I and PGI-C that are only collected at Week 52, an ANCOVA model will be used to analyze the data and adjust for the covariates of baseline MDS-UPDRS I+II+III (continuous) and baseline striatum SBR values (continuous), and baseline PD subtype (categorical).

The Spearman's correlation of change from baseline at Week 52 in each clinical outcome with that of the MDS-UPDRS I+II+III, EP-RPS [REDACTED] will be computed by including and excluding data after PD medication respectively

[REDACTED] [REDACTED]

[REDACTED]

[REDACTED]

[REDACTED]

[REDACTED]

[REDACTED]

[REDACTED]

[REDACTED]

[REDACTED]	[REDACTED]
[REDACTED]	[REDACTED]
[REDACTED]	[REDACTED]
[REDACTED]	[REDACTED]
[REDACTED]	[REDACTED]
[REDACTED]	[REDACTED]
[REDACTED]	[REDACTED]
[REDACTED]	[REDACTED]
[REDACTED]	[REDACTED]
[REDACTED]	[REDACTED]

CONFIDENTIAL

The information contained herein may not be used, disclosed, or published without the written consent of Biogen MA Inc.

--	--

5.3.5 Assessment of the Impact of Covid-19 on the clinical outcome analyses

As this study is on-going when the Covid-19 public health emergency (PHE) occurred, subject visits and data collection were impacted, including missing visits, missed assessments, delayed visits and/or some visits were performed via remote assessments, e.g. telephone/video visits. Every effort was made to document these impacted study activities systematically on the eCRF and other electronic source data.

A complete listing of all visits impacted (e.g. missed visits, delayed or assessment done via remote visits) will be listed in the clinical study report.

In addition, subgroup analyses of the selected key clinical outcome MDS-UPDRS will be performed on a subset of subjects who did not have ≥ 3 consecutive missing doses throughout the study to further evaluate the impact of Covid-19 on the study. The same MMRM model for the primary analyses will be used for the subgroup analyses.

In addition, due to Covid-19, some visits were delayed. A few subjects will have their Week 52 imaging done at later visits up to Week 72 and these will still be considered as Week 52 visit data in the analyses for Week 52. These data were not included in the Week 52 database lock in time, but will be included in the Week 72 database, and the related Week 52 imaging analyses will be updated at the time of the Week 72 interim analyses.

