1 SCOPE OF WORK IN THE STATISTICAL ANALYSIS PLAN

This statistical analysis plan (SAP) only covers the analyses for the placebo-controlled portion of the study (Year 1). Hereafter, the placebo-controlled portion of the study will be referred to as “the study” in the rest of this SAP (e.g., completion of the study means completion of the placebo-controlled portion). A separate SAP will be prepared for the analyses of the dose-blinded extension period and integrated analyses across both portions of the study.

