4 STATISTICAL ANALYSIS METHODS

4.1 General Considerations

This statistical analysis plan (SAP) covers the analyses of the dose-blinded extension (i.e., long term extension) period (Years 2-4) and the analyses across both the placebo-controlled period and the DBE period (analyses integrating the data for Years 1-4).

Summary tables will be presented using descriptive summary statistics. For continuous variables, summary statistics will generally include number of subjects with data, mean, standard deviation, median, 25% percentile, 75% percentile, minimum and maximum. For categorical variables, this will generally include number of subjects randomized or dosed, number with data, and the percent of those with data in each category. Pharmacokinetics (PK) summaries will also include Geometric mean and geometric CV.

Statistical testing will be performed to assess efficacy endpoints by conducting pairwise comparison between each BIIB054 group and the delayed-start group (i.e. subjects who were randomized to placebo in Year-1),. Dose-response relationship may also be tested. Unless stated otherwise, all the statistical tests will be 2-sided with a statistical significance level of 0.05 .

The statistical software, SAS[®] will be used for all summaries and analyses.

Analysis displays

Unless otherwise specified, the analysis of the DBE period and the analyses across both the placebo-controlled period and the DBE period will be displayed by DBE treatment groups as shown below, separate for early and delayed start treatment group) including tables, listings and figures, unless otherwise specified.

Unless otherwise specified, analyses for efficacy data (e.g., pharmacodynamics of imaging, [REDACTED], clinical efficacy, [REDACTED]) will be displayed by the following treatment groups according to randomization assignment at the start of the placebo-controlled period:

- BIIB054 early start: subjects who are assigned to (1) receive BIIB054 in the placebo-controlled period and (2) continue receiving BIIB054 in the DBE period
- BIIB054 late start: subjects who are assigned to (1) receive placebo in the placebo-controlled period and (2) switch to BIIB054 in the DBE period

Unless otherwise specified, analyses for safety, PK, and ADA data will be displayed by the following treatment groups according to dose received:

- BIIB054 early start: subjects who receive BIIB054 in the placebo-controlled period (regardless of randomization assignment)

CONFIDENTIAL

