As this study is on-going when the Covid-19 public health emergency (PHE) occurred, subject visits and data collection were impacted, including missing visits, delayed visits, missed assessments and/or some visits were performed via remote assessments, e.g. telephone/video visits. Every effort was made to document these impacted study activities systematically on the eCRF and other electronic source data.

CONFIDENTIAL

The information contained herein may not be used, disclosed, or published without the written consent of Biogen MA Inc.

	Statistical Analysis Plan Dose Blinded Extension Period	V2.0
---	--	-------------

A complete listing of all visits impacted (e.g. missed visits, delayed or assessment done via remote visits) will be listed in the clinical study report. Missing data due to Covid-19 is considered as missing at random.

Impact of COVID-19 on the clinical outcome analyses

In addition, subgroup analyses of the selected key clinical outcome MDS-UPDRS will be performed on a subset of subjects who did not have ≥ 3 consecutive missing doses throughout the study to further evaluate the impact of Covid-19 on the study. The same MMRM model for the primary analyses will be used for the subgroup analyses.

In addition, due to Covid-19, some visits were delayed. A few subjects will have their Week 52 imaging done at later visits up to Week 72 and these will still be considered as Week 52 visit data in the analyses for Week 52. These data were not included in the Week 52 database lock in time, but will be included in the Week 72 database, and the related Week 52 imaging analyses will be updated at the time of the Week 72 interim analyses.

Impact of COVID-19 on the safety analyses

During the COVID-19 pandemic period, subjects may be prone to a high risk of getting depressed or anxiety. As a result, the analyses below will be performed to evaluate the impact of the COVID-19 pandemic on the safety analyses.

1. An overall summary of AE in DBE period based on data after March 7th, 2020, the start date when subjects in SPARK get impacted by COVID-19
2. An overall summary of AE in the active treatment (placebo-controlled and DBE) period based on data after March 7th, 2020, the start date when subjects in SPARK get impacted by COVID-19
3. AEs by system organ class and preferred term sorted by decreasing frequency in DBE period based on data after March 7th, 2020, the start date when subjects in SPARK get impacted by COVID-19

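### The Covid-19 subset of MDS-UPDRS excludes any run of 3 missed doses, whatever its cause or date, so it does not isolate the impact of Covid-19

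*SAP*

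**What the plan says.** The Year 1 SAP (placebo-controlled period), section 5.3.5, plans a subgroup analysis of MDS-UPDRS in a "subset of subjects who did not have ≥ 3 consecutive missing doses throughout the study", with the purpose "to further evaluate the impact of Covid-19 on the study". The model is the primary one. Section 1 of that SAP fixes the meaning of the last two words of the rule: "Hereafter, the placebo-controlled portion of the study will be referred to as “the study” in the rest of this SAP".

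The extension SAP (dose-blinded extension), section 5, repeats the rule: the analysis is "performed on a subset of subjects who did not have ≥ 3 consecutive missing doses throughout the study". It adds: "The same MMRM model for the primary analyses will be used for the subgroup analyses". That SAP includes "analyses integrating the data for Years 1-4" (section 4.1), and its primary timepoint is Week 72 (section 4.3.2).

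The extension SAP also gives a trial-specific pandemic start, "March 7th, 2020, the start date when subjects in SPARK get impacted by COVID-19", but uses it only for the safety summaries. On records of Covid-19 impact, section 5.3.5 of the Year 1 SAP states: "Every effort was made to document these impacted study activities systematically on the eCRF". Covid-related protocol deviations are identified separately in both plans (Year 1 SAP 5.2.4; extension SAP 4.2.4).

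**The concern.** The stated purpose is to evaluate Covid-19, but the selection rule concerns missed doses in general. A subject who missed three infusions because of an adverse event in 2019 is excluded on the same terms as one whose site closed in spring 2020. The comparison is therefore between all subjects and those without a long dosing gap for any reason.

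The effect is on interpretation. If the subset result differs from the primary result, the difference could be put down to the pandemic when it comes from excluding other interruptions. If the two agree, that does not isolate Covid-19 either. Missed doses occur after randomization and may depend on dose arm. That is a risk; the documents do not show that it happened.

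The extension SAP adds a timing problem. A subject fully dosed up to Week 72 can be excluded from the Week 72 comparison by infusions missed later, which cannot have affected the Week 72 score.

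**Working it through.** **1. The plan's own figure.** Section 6 of the Year 1 SAP projects 78 of 311 subjects through Week 52 by a February 2020 cutoff.
- 78 / 311 = 0.251, which reproduces the stated 25%.
- The last Year 1 infusion is at Week 48, so these subjects have no Year 1 infusion due on or after 7 March 2020. Any run of three missed Year 1 doses among them has another cause, yet it excludes them.
- The denominator is planned enrollment. Against the 357 actually enrolled, the same count gives 78 / 357 = 21.8%.
- This is the share to whom the Year 1 rule cannot properly apply. It is not a count of subjects excluded.

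**2. Year 1 doses due before the pandemic, for everyone.** Section 6 also says that all subjects had completed Week 52 by August 2020. Assume nominal 4-week spacing and a last Week 52 visit between 1 and 31 August 2020.
- Latest first dose: 52 weeks earlier, 3 August to 2 September 2019.
- Study time reached by 7 March 2020: Week 31.0 to Week 26.7.
- Infusions due by then: 8 (Weeks 0 to 28) to 7 (Weeks 0 to 24).

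So at least 7 of the 13 Year 1 infusions were due before the stated pandemic start for every subject. The rule counts them all.

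**3. Doses due after Week 72 in the extension SAP.** Section 2.1 gives 13 doses in Year 1, 12 in Year 2 (Weeks 52 to 96) and up to 16 more in Years 3 and 4.
- Through Week 96: Weeks 76, 80, 84, 88, 92 and 96, or 6 of 25 doses.
- With maximum later dosing: 6 + 16 = 22 of 13 + 12 + 16 = 41 doses (54%).

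The Week 72 analysis waits until all subjects have reached Week 72 (section 4.10), so early enrollees already have later doses due. If the last Week 52 visit fell in August 2020, the last Week 72 visit falls 20 weeks later, from 19 December 2020 to 18 January 2021. A subject at Week 52 on 29 February 2020 would then be at about Week 94 to 98, with at least five infusions due after Week 72. That is enough for a disqualifying run of three.

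**4. Meaning of a missing dose.** Section 5.2.5 of the Year 1 SAP points two ways.
- Overall compliance is measured against all 13 planned doses, whether or not the subject completes. Under that convention a subject who stops after infusion 10 or earlier misses at least 13 − 10 = 3 in a row and is excluded; a stop after infusion 11 or 12 leaves two or one.
- For early withdrawers, expected infusions end at withdrawal, and the percentage taken is counted only up to the last infusion. Under that convention, doses after withdrawal are not missing.

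Neither Covid-19 section says which convention applies.

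**The case against.** The strongest defence is that a cause-neutral subset asks a legitimate question: does the result hold in subjects without long dosing gaps? Nothing in the text labels excluded subjects as Covid-19 cases. That stands as far as it goes, but the plan gives the purpose as Covid-19 impact, and the Year 1 SAP already has an exposure-based set in its per-protocol population (5.1.2 and 5.3.2.9).

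It can also be said that the extension model uses all visits, so a whole-study dosing rule is not plainly mismatched to it. This has some force, but Week 72 is the primary readout of that model and later doses cannot bear on it.

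Two practical objections stand. The eCRF statement concerns affected study activities and does not say that each missed infusion carries a Covid-19 cause. A corrected rule would also still select on dosing after randomization, so it remains supportive.

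Three stronger readings are tempting and not supported:
- A reader might infer that the primary Week 72 result is compromised. It is not: this is an added analysis, the primary analyses use the ITT population, and no alpha depends on the subset.
- A reader might infer that the Year 1 window runs into later years. Section 1 of that SAP limits it to Year 1.
- A reader might infer that all early discontinuers are removed, and size this from the 10% planning dropout as 357 × 0.10 × 10/13 = 27.5 subjects. That needs the 13-dose convention, dropout spread evenly over infusions and no Covid-related stops. The documents establish none of the three.

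**Conclusion.** The concern holds for the supportive Covid-19 subset only. In both SAPs, followed as written, the rule excludes interruptions unrelated to Covid-19 and those before 7 March 2020, so the subset cannot isolate the impact of the pandemic. On the plan's projection, about a quarter of subjects could have no Covid-missed Year 1 dose, and on the nominal schedule at least 7 of 13 Year 1 infusions predate the pandemic for everyone. In the extension SAP alone, between 6 of 25 and 22 of 41 scheduled doses fall after Week 72 and could exclude a subject from the supportive Week 72 comparison; at the Week 72 data cut only those already due would count.

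Removal of discontinuers is a possible reading, not a certain one. Neither its size nor the total number wrongly excluded can be computed from the documents. The correction is worthwhile because it is cheap and the analysis otherwise does not answer its stated question.

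**What to change.** In each SAP, define the subset as subjects without 3 or more consecutive missed infusions, counting only infusions that were:
- due on or after 7 March 2020;
- due before the analysed timepoint (Week 52 in the Year 1 SAP, Week 72 in the extension SAP); and
- recorded as Covid-19 related, on the eCRF or in the Covid-19 protocol-deviation category, where that attribution is available.

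State that infusions not given after permanent discontinuation for reasons other than Covid-19 do not count as missing.

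The cost is a short change of wording in each SAP and a revised subset flag, using records the plans describe as collected. Attribution may be incomplete for some missed infusions; for those, the date and timepoint limits alone serve as the fallback. If doses after stopping are otherwise counted alike, the subset can only stay the same size or grow.
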